## 5.2 Study conclusion

Upon study conclusion (52 weeks post-vaccination), the investigators will:

- Review data collected to ensure accuracy and completeness
- Complete the Study Conclusion screen in the eCRF.

# 6. STUDY PRODUCT AND ADMINISTRATION

## 6.1 Description of Study Product

Recombinant Novel Coronavirus Vaccine (Adenovirus Type 5 Vector). This vaccine, Ad5-nCoV, is a replication-defective recombinant human type 5 adenovirus expressing novel coronavirus S protein, which is produced by viral amplification in HEK293SF-3F6 cells, purification and formulation with addition of proper excipients. The product is used for prevention from infection caused by novel coronavirus.

**Active Ingredients:** Replication-defective recombinant human type 5 adenovirus expressing S protein of novel coronavirus

**Excipients:** Mannitol, sucrose, sodium chloride, magnesium chloride, polysorbate 80, HEPES, and glycerin

**Packaging:** The vaccine is contained in a vial.

**Specification:** 0.5 mL/vial

**Dosage**  $5 \times 10^{10}$  vp ( $\geq 4 \times 10^{10}$  vp)

\* Explanatory note: The vials contain a volume of 0.5 ml. The indication is to administer this amount. The manufacturer of the vaccine has advised that a volume between 0.4 ml and 0.5 ml per dose is permitted since it has been calculated that the 0.4 ml extractable volume of each vial in the lot involved in this study (Lot NCOV202103006) has met the requirements of the study based on good vaccination practices. The vaccines used in this study have passed the quality control procedure during the filling process and the fill volume of the vaccines meets the quality standards.

**Shelf Life:** Tentatively 24 months

**Storage:** This vaccine should be stored and transported at 2-8°C.

**Administration:** Intramuscular injection in the deltoid muscle of the upper arm.

**Schedule:** A double-dose of active vaccine is planned for all participants. A second dose of active vaccine is planned for all participants 56 days after the first Injection.

**Manufacturer:** CanSino Biologics Inc.  
[name]  
Postal code: 300462  
[contact]  
[contact]  
Website: [www.cansinotech.com](http://www.cansinotech.com)

**Developers:** CanSino Biologics Inc.  
Beijing Institute of Biotechnology

### **Contraindications to the Study Vaccine**

- (1) Allergic reaction to any component of this vaccine.
- (2) Acute illness, acute phase of chronic disease, and fever.
- (3) Pregnant and lactating women.
- (4) People with thrombocytopenia or hemorrhagic diseases, immune-suppressive therapy or immune dysfunction, and uncontrolled seizure disorder and other progressive neurological disorders.

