Exclusion criteria	
Exclusion Criteria
 

• Participation in any other COVID-19 prophylactic drug trials for the duration of the study.

○ Note: Participation in COVID-19 treatment trials is allowed in the event of hospitalization due to COVID-19. The study team should be informed as soon as possible.

• Planned receipt of any vaccine (licensed or investigational), other than the study intervention, within 14 days before and after study vaccination.

• Prior receipt of an investigational or licensed vaccine likely to impact on the interpretation of the trial data (e.g. Adenovirus vectored vaccines, any coronavirus or SARS vaccines)

• Administration of immunoglobulins and/or any blood products within the three months prior to the planned administration of the vaccine candidate.

• Any confirmed or suspected immunosuppressive or immunodeficient state; asplenia; recurrent severe infections and chronic use (more than 14 days) of immunosuppressant medication within the past 6 months. Topical steroids or short-term (course lasting ≤14 days) oral steroids are not an exclusion.

• Active opportunistic infections or other AIDS-defining illness in the last six months.

• History of allergic disease or reactions likely to be exacerbated by any component of Ad5-nCoV

• Any history of angioedema

• Any history of anaphylaxis to any vaccine component

• Pregnancy, lactation or willingness/intention to become pregnant within 90 days after receiving study vaccine

• Current diagnosis of or treatment for cancer (except basal cell carcinoma of the skin and cervical carcinoma in situ)

• History of serious psychiatric condition likely to affect participation in the study

• Bleeding disorder (e.g. factor deficiency, coagulopathy or platelet disorder), or prior history of significant bleeding or bruising following IM injections or venepuncture

• Suspected or known current alcohol or drug dependency

• Severe and/or uncontrolled cardiovascular disease, respiratory disease, gastrointestinal disease, liver disease, renal disease, endocrine disorder and neurological illness (mild/moderate well-controlled comorbidities are allowed)

• History of laboratory-confirmed COVID-19

• Continuous use of anticoagulants, such as coumarins and related anticoagulants (i.e. warfarin) or novel oral anticoagulants (i.e. apixaban, rivaroxaban, dabigatran and edoxaban)

• Any other significant disease, disorder or finding which, in the opinion of the investigator, may significantly increase the risk to the volunteer because of participation in the study, affect the ability of the volunteer to participate in the study or impair interpretation of the study data.

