In its original version, the protocol limited inclusion to "people living with HIV on stable treatment and virologically suppressed..." .

Likewise, the design was double-blind versus placebo in a 2:1 ratio.

The advancement of the national vaccination reduced the possibilities of access to the study under such design, for which this protocol amendment was proposed.

Volunteers initially included in the study will receive two doses of the vaccine and will continue their follow-up as established in the protocol.

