## **4. STUDY POPULATION**

The trial will recruit 500 participants, 18 years of age and older, living with HIV. Recruitment should support the generalizability of results, including by important characteristics such as age (including elderly). Participants must meet inclusion/exclusion criteria.

Participants will be enrolled at 4 study sites in Argentina. Depending on success of participant enrolment, as well as the COVID-19 attack rate, this list may be revised to include additional sites.

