#### **4.1 Inclusion Criteria**

1. Adults of 18 years of age, and older, with confirmed HIV infection according to criterion 2.
2. A positive rapid test or ELISA and/or a plasma HIV-1 viral load >1000 copies/ml or rapid test or ELISA plus a positive Western Blot test. In patients on antiretroviral treatment, a medical history summary or prescription signed and stamped by the treating physician is acceptable. Able and willing (in the Investigator's opinion) to comply with all study requirements.
3. Willing to allow the investigators to discuss the volunteer's medical history with their General Practitioner/personal doctor and access all medical records when relevant to study procedures.
4. Healthy adults, or stable-healthy adults who may have a pre-existing medical condition that does not meet any exclusion criteria. A stable medical condition is defined as disease not requiring significant change in therapy or hospitalization for worsening disease during the 3 months before enrolment [4].
5. For subjects of childbearing potential only: Willingness to practice continuous effective contraception (see glossary) for 30 days prior to enrolment in the study, for 90 days after receiving vaccination during the study, and have a negative pregnancy test on the day(s) of screening/ vaccination (First Injection Visit and Second Injection Visit).
6. Males participating in this study who are involved in heterosexual sexual activity must agree to practice adequate contraception (see glossary) and refrain from donating sperm for 90 days after receiving the study vaccination.
7. Agreement to refrain from blood donation during the study.
8. Provide written informed consent.

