#### **4.2 Exclusion Criteria**

1. Participation in any other COVID-19 prophylactic drug trials for the duration of the study.  
*Note: Participation in COVID-19 treatment trials is allowed in the event of hospitalization due to COVID-19. The study team should be informed as soon as possible.*
2. Planned receipt of any vaccine (licensed or investigational), other than the study intervention, within 14 days before and after study vaccination.

3. Prior receipt of an investigational or licensed vaccine likely to impact on the interpretation of the trial data (e.g. Adenovirus vectored vaccines, any coronavirus or SARS vaccines).
4. Administration of immunoglobulins and/or any blood products within the three months prior to the planned administration of the vaccine candidate.
5. Any confirmed or suspected immunosuppressive or immunodeficient state (other than living with HIV, on stable treatment, and virologically suppressed for at least 6 months); asplenia; recurrent severe infections and chronic use (more than 14 days) of immunosuppressant medication within the past 6 months. Topical steroids or short-term (course lasting  $\leq$ 14 days) oral steroids are not an exclusion.
6. Active opportunistic infections or other AIDS-defining illness in the last six months.
7. History of allergic disease or reactions likely to be exacerbated by any component of Ad5-nCoV.
8. Any history of angioedema.
9. Any history of anaphylaxis to any vaccine component.
10. Pregnancy, lactation or willingness/intention to become pregnant within 90 days after receiving study vaccine.
11. Current diagnosis of or treatment for cancer (except basal cell carcinoma of the skin and cervical carcinoma in situ).
12. History of serious psychiatric condition likely to affect participation in the study.
13. Bleeding disorder (e.g. factor deficiency, coagulopathy or platelet disorder), or prior history of significant bleeding or bruising following IM injections or venepuncture.
14. Suspected or known current alcohol or drug dependency.
15. Severe and/or uncontrolled cardiovascular disease, respiratory disease, gastrointestinal disease, liver disease, renal disease, endocrine disorder and neurological illness (mild/moderate well-controlled comorbidities are allowed).
16. History of laboratory-confirmed COVID-19.
17. Continuous use of anticoagulants, such as coumarins and related anticoagulants (i.e. warfarin) or novel oral anticoagulants (i.e. apixaban, rivaroxaban, dabigatran and edoxaban).

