Approximately 25 mL of whole blood will be collected from each participant at First Injection Visit and separated for serum. The serum will be aliquoted. The first aliquot will be used to measure for baseline antibodies against SARS-CoV-2. Presence of pre-existing SARS-CoV-2 antibodies found in baseline serum will be used for a stratified immunogenicity and efficacy sub-analysis. The second aliquot will be stored as a back-up. In participants who entered in the blind version and then were unblinded and vaccinated, baseline serology will not be performed again, taking the values of the baseline visit performed in the first visit.

- **Blood collection for ELISpot and ICS measurement**

In a subset of approximately 50 participants, approximately 30mL of whole blood will be collected from participants, in addition to the 25mL being collected for ELISA antibody analysis. TNF, IL-4, IL-5, IL-13 will be measured by ICS on first-injection day, Day 28, Day 84 and Weeks 24 and 52 after vaccination. PBMC will be shipped on dry ice to Nexelis Laboratories (Canada).

- **Check contraindications, warnings and precautions to injection**

Contraindications, warnings and precautions to injection must be checked at the beginning of each Injection Visit.

- **Urine Pregnancy Test/Birth Control**

Women of child-bearing age will be asked to perform a urine pregnancy test before each Injection Visit. The result of the urine pregnancy test must be negative in order to proceed with vaccine administration. In addition, participants who are able to become pregnant or could impregnate a partner are required to have used approved contraception least 30 days prior to the study vaccination and for 90 days after the study vaccination.

- **Assess pre-injection vital signs (body temperature, blood pressure, pulse rate and respiratory rate)**

Body temperature of all participants needs to be measured prior to any study product administration. Body temperature may be measured by any method (oral, axillary). If the

participant has fever (fever is defined as temperature  $\geq 38.0^{\circ}\text{ C}$  orally or  $\geq 37.8^{\circ}\text{ axillary}$ ) on the day of injections, the injection visit will be rescheduled within 1 week.

- **Screening conclusion**

Participants will be deemed eligible to participate upon reviewing medical history and inclusion and exclusion criteria. This will occur prior to vaccination at First and Second Injection Visit.

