### Contraindications to administration of the investigational product at First Injection Day

The following events constitute contraindications to administration of the study products at that point in time. If any contraindication is present at the time scheduled for injection, the participant may be injected at a later date, within the time window specified in the protocol, or withdrawn at the discretion of the investigator.

- Acute disease and/or fever at the time of administration.
- Fever is defined as temperature  $\geq 38.0^{\circ}\text{C}$ , taken orally.
- Participants with a minor illness (such as mild diarrhea, mild upper respiratory infection) without fever can be administered the product.

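### The protocol does not settle whether people with untreated or unsuppressed HIV may be enrolled, and a primary viral-load endpoint changes meaning with the answer

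*Protocol*

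**What the plan says.** Every participant has HIV; Section 4 states: "The trial will recruit 500 participants, 18 years of age and older, living with HIV". Five places bear on which people with HIV may be enrolled and dosed.

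- **Section 4.2, item 5** excludes immunosuppressive or immunodeficient states, with an exception in parentheses: "other than living with HIV, on stable treatment, and virologically suppressed for at least 6 months".
- **Synopsis, Exclusion criteria**, gives the same criterion without the parenthesis: "Any confirmed or suspected immunosuppressive or immunodeficient state; asplenia".
- **Section 1.3, closing paragraphs**, opens "In its original version, the protocol limited inclusion to" and then names people on stable treatment with virological suppression. It explains that national vaccination had reduced access to the study under that design, hence the amendment. It does not state what the suppression rule is now.
- **Section 1.3, earlier paragraph**, describes the vaccinated population as on stable treatment and does not mention suppression.
- **Section 6.1, Contraindications to the Study Vaccine, item 4**, includes "immune-suppressive therapy or immune dysfunction". It neither defines the term nor mentions HIV.

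These texts are operative. Section 5.1 requires that "Contraindications, warnings and precautions to injection must be checked at the beginning of each Injection Visit", and it has the inclusion and exclusion criteria reviewed again at the second injection visit.

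Section 9.3.3 lists among the primary safety endpoints the incidence of a detectable viral load at 24 and 52 weeks. It sets no condition on viral load at entry.

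**The concern.** The synopsis and Section 4.2 give two forms of one exclusion criterion, and they differ on the characteristic that varies most within an all-HIV population: whether the infection is treated and suppressed. A site working from Section 4.2 would turn away a viraemic candidate. A site working from the synopsis, and taking HIV as implicitly exempt because the trial requires it, would not. Section 1.3 makes it harder to choose, because it suggests that the parenthesis in Section 4.2 could be a remnant of the version before the amendment.

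Two things are at stake. The first is an unresolved instruction on who may receive the vaccine. The second is what a primary endpoint measures. In a suppressed cohort, a detectable viral load at follow-up signals loss of control after vaccination. In a mixed cohort it also counts people who were viraemic before the first injection.

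**Working it through.** There is no plan figure to reproduce, since Section 9.1 declines to set a statistical sample size. The check is a comparison of the texts, followed by the consequence for the endpoint.

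**Step 1: what each text implies for eligibility on this ground alone.**

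| Text | HIV treated and suppressed for 6 months | HIV untreated or viraemic |
|---|---|---|
| 4.2 item 5 | exempt from the exclusion | outside the exception |
| Synopsis, HIV taken as implicitly exempt | eligible | eligible |
| Synopsis, read literally | no exception | no exception |
| 1.3, population sentence | within the description | untreated is outside it; suppression not mentioned |
| 1.3, amendment paragraphs | eligible | limit assigned to the original version; current rule not stated |
| 4.1 item 2 | silent on suppression | silent on suppression |
| 6.1 item 4 | undefined, HIV not named | undefined, HIV not named |
| 6.2 lists for each injection day | not a bar | not a bar |

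Neither reading of the synopsis separates people by suppression; Section 4.2 does. The right-hand column therefore has no single answer. The lists for the two injection days in Section 6.2 open with "Acute disease and/or fever at the time of administration" and nowhere mention immune dysfunction, so they do not settle the matter either.

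**Step 2: effect on the primary viral-load endpoint.** Section 9.2.1 defines the intent-to-treat cohort as everyone given at least one injection, and Section 9.3.3 analyses proportions in it. Among participants with a value at a given visit, let:

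- u = number undetectable at entry and d = number detectable at entry;
- a = number of the u who are detectable at the visit;
- b = number of the d who are still detectable at the visit.

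The endpoint as worded gives (a + b) / (u + d). The proportion describing new viraemia is a / u.

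- If Section 4.2 is applied and entry values are undetectable, d = 0 and b = 0, and the two quantities coincide.
- If viraemic people are enrolled and nobody loses control, a = 0. The endpoint then equals b / (u + d), which can be as large as v = d / (u + d), the viraemic share at entry. None of that would have arisen after vaccination.
- If viraemic participants start or change treatment during follow-up, b falls, and the proportion moves for reasons unrelated to the vaccine.

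The documents give no value for v, so none is inserted. Section 9.1 calls the study open and non-comparative, so no concurrent control would show how much of the proportion was present at entry.

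**Step 3: consistency over calendar time.** Under the limit that Section 1.3 describes, people enrolled before the amendment were to be suppressed, and Section 3.2 keeps them in the study. If the limit has since been lifted, d may be concentrated among later entrants.

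**The case against.** The strongest reply is that the protocol should be read as a whole. The trial requires HIV, so HIV as such cannot be the excluded state in the synopsis or the contraindicated one in Section 6.1. This stands for HIV as such. It does not say whether untreated or viraemic HIV shares that implied exemption, and Section 4.2 indicates that it does not.

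Three stronger inferences are tempting and should not be drawn.

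- **That inclusion criterion 2 contradicts Section 4.2.** Section 4.1 mentions "a plasma HIV-1 viral load >1000 copies/ml", but as one way of confirming the diagnosis. Section 5.1 allows verification from an earlier serology result or an earlier detectable viral load. A person suppressed for six months can meet both criteria, so they can be applied together.
- **That Section 6.1 or the synopsis could bar all 500 participants.** The wording in 6.1 is generic and undefined, and the injection-day lists in Section 6.2 omit it. A site reading the whole protocol would not conclude that nobody may be dosed. What remains is a need for clarification.
- **That a definite number of participants is affected.** The documents give no viraemic share. Applying an assumed share of candidates to 500 enrolled people would also mix denominators, since candidates screened out are replaced by others.

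It is fair to add that Section 1.3 partly describes superseded text, so it hints that the parenthesis is a remnant without proving it. Divergence between sites is possible rather than shown: Section 4 plans four sites in one country, and Section 14.2 has monitors checking enrolment against the protocol. Monitors face the same conflicting texts, however.

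Finally, Section 5.1 makes the screening viral load the reference for later comparison, so suppression at entry will be known, and incidence could be read as new onset. The data do exist. The endpoint wording does not state that restriction.

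**Conclusion.** The point holds as an inconsistency in current text, with a consequence for a primary endpoint. Section 4.2 item 5 and the synopsis differ on the same exclusion criterion, and Section 1.3 casts doubt on which is intended. The protocol therefore does not say whether viraemic or untreated people may be enrolled. The unqualified contraindication in Section 6.1 is a secondary matter of the same kind.

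The effect on the viral-load endpoint is bounded above by the share of analysed participants who are viraemic at entry. It is nil if that share is zero and cannot be given a number from the documents. The conclusion assumes that the endpoint is computed as worded, over everyone with a value, and that some viraemic people could enter under the wider reading. No view is taken on which eligibility or dosing rule is right; the passages must be reconciled.

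**What to change.** The sponsor should reconcile the synopsis exclusion list, both statements in Section 1.3, Section 4.2 item 5 and Section 6.1 item 4 into one statement on HIV and viral suppression. The sponsor should take the clinical decision and repeat the result in the same words wherever the criterion appears. Section 6.1 should say how its contraindication applies to a population that has HIV by definition, and how it relates to the injection-day lists in Section 6.2.

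If viraemic people are or were eligible, the viral-load endpoint and the immunogenicity results should be reported by suppression at entry, and Section 9.3.3 should say whether its endpoint counts people already detectable at entry. Table 1 already collects a viral load at Visit 1. Table 2 schedules no new one at Visit 1.B for former placebo recipients, so their value from study entry would serve.

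The cost is a wording amendment and an added breakdown in existing tables. No new visit or sample is needed.

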### **Warnings and Precautions**

1. This vaccine is strictly prohibited to be administered by intravascular injection.
2. Epinephrine and other drugs as well as equipment should be in place when the vaccine is used, in case emergency treatment of severe allergic reactions will be needed. Those who are immunized with this vaccine should be observed for at least 30 minutes at the site.
3. As with all vaccines, this vaccine may not produce 100% protection in the vaccinated population.
4. The vaccine must be stored in the place not accessible by children.
5. The vaccine should be shaken before injection. It should not be used under following circumstances: presence of foreign objects, cracked vaccine syringe, unclear or expired label, or any other abnormal appearance of the vaccine.
6. No disinfectant in contact with the vaccine when injection.

